7.5.1.2.4 Action taken with study treatment

Any action on study treatment to resolve the AE is to be documented using the categories listed below.

- Device use stopped
- Device use interrupted
- No change
- Not applicable

7.5.1.2.5 Other specific treatment(s) of adverse events

- None
- Remedial drug therapy
- Other

7.5.1.2.6 Outcome

The outcome of the AE is to be documented as follows:

- Recovered/resolved without sequelae
- Recovered/resolved with sequelae
- Not recovered/not resolved (ongoing)
- Fatal
- Unknown

7.5.1.3 Assessments and documentation of adverse events

The investigator has the obligation to report AEs. All non-serious events will be assessed and recorded during the specified observational phase (from signing the informed consent form up to 30 [+5] days after last study medication intake), whether believed to be related or unrelated to the treatment. AE forms will be included. The record will include clinical symptoms or final diagnosis when available, date of appearance, duration, severity and relationship to treatment. A record will also be kept of the action taken and the follow-up until resolution of the AE.

7.5.1.4 Reporting of serious adverse events

Notification of the IECs / IRBs

Notification of the IECs / IRBs about all relevant events (e.g., SAEs, suspected, unexpected, serious adverse reactions [SUSARs]) will be performed by the investigator according to all applicable regulations the serious criteria (as defined in Section [7.5.1.1](#)) are applicable.

7.6 OTHER PROCEDURES AND VARIABLES

7.6.1 Raynaud's attacks assessment

Raynaud's attacks will be assessed using the composite of the following 6 individual outcome measures in order to minimize the measurement variability and placebo response(7): Raynaud's condition score, patient assessment of Raynaud's phenomenon, physician assessment of Raynaud's phenomenon, attack symptoms, duration of attacks, and number of attacks per day.

The Raynaud's condition score is a daily patient assessment of Raynaud's phenomenon activity using a 0-10 ordinal scale. It incorporates the cumulative frequency, duration, severity and impact of Raynaud's phenomenon attacks, reflecting the overall degree that Raynaud's has affected use of the participant's hands. The Raynaud's condition score, along with details of the frequency and duration of Raynaud's attacks, will be incorporated into the daily diary that participants will be asked to complete for 1 week (7 days) at the time points shown below.

The patient and physician assessment assesses the severity of Raynaud's phenomenon in the past week using a 0-100 VAS.

Frequency: The diary is to be completed by participant for one-day during the observation period, and one-day at the end of study (to occur the day prior to end of study visit).

7.6.2 Quick Inventory of Depressive Symptoms (QUIDS-SR)

The QUIDS-SR is a 16-item questionnaires that evaluates depression. The QUIDS-SR has been validated and used to screen, diagnose, monitor and measure the severity of depression.

7.6.3 Patient-Reported Outcomes (PROs) / Health-Related Quality of Life (HRQoL) questionnaires

Three patient-reported outcomes (PROs)—the HAQ-DI/SHAQ, and PROMIS-29— will be completed by all participants in the study.

Scleroderma Health Assessment Questionnaire (HAQ-DI/SHAQ)

The HAQ-DI consists of 8 domains from the Health Assessment Questionnaire disability index, a HRQoL instrument that measures self-reported function in 8 domains of activity in 20 weighted responses and a VAS of pain experienced in the past week. It additionally measures 5 domains specific to scleroderma using a continuous VAS: Raynaud's phenomenon, digital tip ulcers, lung symptoms, gastrointestinal symptoms, and a global patient assessment. The VAS subscales of the SHAQ were shown to be significantly correlated with objective parameters and were responsive to change in a cohort and in a Raynaud's phenomenon trial in SSc. The SHAQ requires approximately 5 minutes to complete.

Patient-Reported Outcomes Measurement Information System (PROMIS)-29

The PROMIS-29 is a validated instrument to measure the health status of SSc patients, demonstrating moderate to high correlation with other instruments validated in SSc, including the SF-36 physical component score and HAQ-DI. It incorporates 7 core domains from the PROMIS questionnaire, which specifically relate to physical, mental, and social health aspects of chronic illness: pain, fatigue, depression, anxiety, sleep, and physical function, as well as one 11-point rating scale for pain intensity. It contains 8 items with 29 weighted responses in total,

and requires approximately 5 minutes to complete.

7.6.4 Participant and Physician Global Assessment

A global assessment for patient and physician will be obtained.

The participant assessment represents the patient's assessment of the patient's global scleroderma on a 0-10 Likert scale. "On a scale of 0-10, how was your overall health in the last week? 0=Excellent; 10=Extremely Poor. The physician global assessment represents the physician's assessment of the patient's current disease activity on a 0-10 Likert scale. "On a scale of 0-10, how was your patient's overall health in the last week? 0=Excellent; 10=Extremely Poor". Both assessments are made at baseline and Week 16, OLE Week 0 and OLE Week 16.

8. Statistical methods and determination of sample size

8.1 General considerations

This section presents a summary of the planned statistical analyses. A statistical analysis plan (SAP) will be written for the study that contains detailed descriptions of the analyses to be performed. The SAP will be finalized prior to unblinding of the data.

Continuous variables will be summarized using descriptive statistics including n, mean, median, standard deviation, range (e.g., minimum and maximum). Qualitative variables will be summarized using counts and percentages. Graphical methods will be used in this pilot study to assess the pattern of response over time for key variables and to assess the relationships among variables.

Unless otherwise specified, statistical analyses will be performed using SAS Version 9 or higher. Where appropriate, statistical tests will be conducted at the 0.05 significance level (with no adjustments for multiplicity) using two-tailed tests and p-values will be reported.

Given the rare nature of SSc and the consequent small sample size for this pilot study, the statistical power of any comparisons is limited (i.e., there is sufficient power to detect only large treatment differences). As such the analysis will be largely descriptive in nature. The p-values resulting from formal statistical tests will be interpreted from a hypothesis-generating, rather than a confirmatory framework.

Analysis sets

As this is an open-label study, all participant who have used the Apollo system wearable for at least one dose (one day) will be analyzed. The primary endpoint and all secondary outcomes will be assessed using this analysis set.

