An Open-Label Study of the Apollo Device for Fatigue in Systemic Sclerosis

Test device: Apollo

Study purpose: Evaluate the efficacy and use patterns of Apollo

Clinical study phase: II

Version no: 1

Version Date February 1, 2021

Sponsor Investigator:

The study will be conducted in compliance with the protocol, ICH-GCP and any applicable regulatory requirements.

Confidential

The information provided in this document is strictly confidential and is intended solely for the guidance of the clinical investigation. Reproduction or disclosure of this document - whether in part or in full - to parties not associated with the clinical investigation, or its use for any other purpose, without the prior written consent of the sponsor is not permitted.

Throughout this document, symbols indicating proprietary names (®, TM) may not be displayed. Hence, the appearance of product names without these symbols does not imply that these names are not protected.

Synopsis

Title	An Open-Label Study of the Apollo Device for Fatigue in Systemic Sclerosis
Short title	The Apollo in Systemic Sclerosis
Clinical study phase	II
Study objective(s)	The primary objective of this study is to provide preliminary data on the tolerability and efficacy of the Apollo system for the management of fatigue in systemic sclerosis.
Test device	Apollo System
Mechanism of use	The Apollo system consists of a wearable device whose frequency of use is controlled by the participant. The participant will install the study mobile application on a mobile device of their choosing. The wearable device is controlled by the mobile app through which the participant can choose when and for how long to use it.
Location of use	Wrist or ankle
Duration of use	4 weeks
Background treatment	Patients will continue any existing prescription medication, including prednisone and immunosuppressives, at steady doses for 4 weeks prior to baseline (visit 1) and during the four-week intervention period.
Indication	Scleroderma-associated fatigue

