2. STUDY OBJECTIVES

The primary objective of this study is to provide preliminary data on the efficacy and tolerability of the Apollo device in the management of fatigue in SSc.

The primary efficacy outcome is the change from baseline to four weeks of intervention using the Apollo system in the PROMIS-Fatigue scale. This instrument that has been previously validated in multiple diseases.

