2.1 Secondary objectives

The secondary objectives of this study are to provide preliminary data on indices of depression, health-related quality of life, Raynaud symptoms and tolerability/frequency of use with the Apollo device in SSc.

Specific secondary objective measures include:

- Depression, measured by the QUIDS-SR (16 item) score.
- Health-related quality of life (HRQOL) using PROMIS-29
- HAQ-DI
- Visual analog scales from scleroderma-health assessment questionnaire (SHAQ) assessing burden of digital ulcers, Raynaud's disease, gastrointestinal involvement, breathing, and overall disease
- Improvement of Raynaud's phenomenon (RP) (7, 8)
 - Raynaud's condition score
 - Raynaud visual analog scale
 - Patient and physician assessment of RP; pain, numbness, and tingling
 - RP frequency and duration of attacks based on one-day use of the Raynaud application used at baseline and two weeks.
-

3. INVESTIGATORS and PERSONNEL

Role: Investigator
Name and Contact Information: [name], MPH
University of Pittsburgh School of Medicine
[name]
[name]
[name]
[contact]
Email: [contact]

Role: Research coordinator
Name and Contact Information: [name], BA
University of Pittsburgh School of Medicine
[name]
[name]
[name]
[contact]
Email: [contact]

Role: Graduate student / research assistant
Name and Contact Information: [name]

Data Safety and Monitoring Plan

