4.1.2 Intervention Phase

At the baseline visit, participants who have met all of the inclusion criteria. At this visit they will complete the following questionnaires:

- 1) PROMIS-fatigue
- 2) PROMIS-29
- 3) The QUIDS-SR
- 4) HAQ-DQ with SHAQ
- 5) Raynaud condition score, Raynaud visual analog scale and digital ulcer visual analog scale

They will then be provided the wearable Apollo system device. They will download the mobile application, and be taught how to install it and use it to control the wearable Apollo device by the research coordinator(s). Any questions will be answered at this time. Participants will be able to use the device from the time they leave the visit. Use of the device will be entirely at the subject's control.

In the week prior to their end-of-study visit, participants will complete a daily diary collection of Raynaud attack episodes and symptoms using the paper diary form. This will be provided prior to leaving the baseline visit.

Participants will be sent a reminder call or text the day before and day they are to begin their diary collection on one week prior to their scheduled end-of-study visit.

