7.1.2.2 Visit 1 – Baseline

The following assessments will be performed at the Baseline visit

- Reconfirmation of eligibility
- PROMIS-fatigue scale administered
- Patient reported outcomes (QUIDS-SR, patient global assessment, PROMIS-29, HAQ-D1/SHAQ, visual analog scales) and physician global assessment
- Vital signs (blood pressure and heart rate). The blood pressure is measured in a sitting

position after the participant has been at rest for at least 5 minutes. The same arm is always used for these measurements

- Digital ulcer assessment
- Assessment of Raynaud attacks – participant provided the one-day diary and RCS to complete the day following the screening
- Recording and assessment of AEs (see Section [7.5.1.3](#))
- Downloading of the mobile application and teaching of how to use the Apollo wearable device. The participants will be allowed to use it up to 30 minutes to familiarize themselves with the working of the device while at this visit.

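### The only analysis set admits people with at least one day of device use, so complete never-users can drop out of the use and tolerability summaries

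*Combined protocol and SAP*

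**What the plan says.** The analysis-set paragraph in section 8.1 states that "all participant who have used the Apollo system wearable for at least one dose (one day) will be analyzed". The next sentence gives its scope: "The primary endpoint and all secondary outcomes will be assessed using this analysis set". No set of all enrolled participants, or of all participants given the device, is defined anywhere.

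Use of the device is one of the things under study. The title page gives the purpose as "Evaluate the efficacy and use patterns of Apollo". Section 2 sets out to "provide preliminary data on the efficacy and tolerability of the Apollo device in the management of fatigue in SSc". Section 2.1 adds, among the secondary aims, "Raynaud symptoms and tolerability/frequency of use with the Apollo device in SSc".

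The protocol requires no minimum use. Section 4.1.2 says: "Use of the device will be entirely at the subject's control". Section 6.5 has the system record use for each subject. Sections 4.1.3 and 6.5 keep people who cut down or stop in the study through the final visit.

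At the baseline visit (section 7.1.2.2), "The participants will be allowed to use it up to 30 minutes to familiarize themselves with the working of the device while at this visit". The plan does not say whether that session satisfies the one-dose, one-day requirement, and it does not define a dose for this device.

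**The concern.** Where use is voluntary and use patterns are a study aim, zero is a legitimate value of the outcome. A set restricted to people with some use selects on the quantity being measured, so a participant who takes the device home and never switches it on is removed when they should be counted as zero. How many people took the device up then cannot be estimated from the set, and average use is computed on a denominator that is too small. Someone who declines to wear the device at all also disappears from the tolerability summary, although that refusal is informative.

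The undefined dose adds a second difficulty. Depending on whether the clinic session counts, the same sentence excludes either almost nobody or every complete non-user at home. Section 8.1 ties completion of the detailed SAP to unblinding, but section 6.2 says nothing is blinded. That milestone therefore does not ensure the choice is made before the usage logs are seen.

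**Working it through.** The plan gives no figure for non-use, so there is none to reproduce.

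**Inputs**
- N = 30 participants (section 4.1).
- Expected mean improvement of about 5 T-score points and SD of about 5 (Synopsis, plan for statistical analysis).
- k = number of complete never-users. This is an assumption; the range shown is 0 to 5 of 30.
- Mean PROMIS-Fatigue improvement of 5 in users and 0 in never-users. The 0 is an assumption.
- Reading tested: the clinic familiarisation session does not count as use.

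**Formulas**
- Ever-use share among all given the device: (30 − k)/30. In the set as written it is (30 − k)/(30 − k) = 100% for every k.
- Mean use: if total logged use is U, the set as written gives U/(30 − k) and the full denominator gives U/30. The ratio is 30/(30 − k).
- Mean fatigue improvement among all given the device: 5 × (30 − k)/30. The shift from 5 is 5k/30.

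| k (assumed) | Ever-use, all given device | Ever-use, set as written | 30/(30 − k) | Mean use overstated by | Mean improvement, all given device | Shift |
|---|---|---|---|---|---|---|
| 0 | 100% | 100% | 1.000 | 0% | 5.00 | 0.00 |
| 1 | 96.7% | 100% | 1.034 | 3.4% | 4.83 | 0.17 |
| 2 | 93.3% | 100% | 1.071 | 7.1% | 4.67 | 0.33 |
| 3 | 90.0% | 100% | 1.111 | 11.1% | 4.50 | 0.50 |
| 4 | 86.7% | 100% | 1.154 | 15.4% | 4.33 | 0.67 |
| 5 | 83.3% | 100% | 1.200 | 20.0% | 4.17 | 0.83 |

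**How likely is any never-user?** With a true never-use rate p (assumed), the chance of at least one among 30 is 1 − (1 − p)^30. This is 26% at p = 1%, 79% at 5% and 96% at 10%.

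**Scale of the fatigue shift.** The standard error of the mean change on the planning figures is 5/√30 = 0.91, so even the k = 5 shift of 0.83 is below one standard error.

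**Power.** A two-sided paired t-test at 0.05 with effect size 1 has power 99.96% at n = 30 and 99.8% at n = 25. (The Synopsis states 86% for n = 30, which this calculation does not reproduce; that is a separate matter.) Losing a few never-users is a question of bias, not of power.

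**If the clinic session does count as use**, everyone who tries the device at Visit 1 is in the set, almost nobody is excluded, and the overstatement is close to 0%.

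**The case against.** Several counter-arguments have force.

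- **The exclusion may be almost empty.** Participants are taught to use the device at Visit 1 and may try it there. If that is a dose, nearly everyone qualifies. This stands as a limit on the finding. It does not remove it, because the session is optional and the plan does not say that it counts.
- **Whether the set governs use data is partly inferred.** Frequency of use and tolerability appear in the general statement of section 2.1, but not in its list of specific measures or in section 7.3. The change-from-baseline analysis in section 8.2.2 does not suit a usage log. This is fair. Still, section 8.1 covers all secondary outcomes and offers no other set, so the literal reading is the restrictive one.
- **Safety reporting.** A reader might infer that never-users vanish from the adverse-event tables. The documents do not support that: section 8.3.3 names no population, and section 7.5.1.3 records non-serious events from the signing of consent.
- **Early rejecters.** A reader might also infer that anyone who tries the device and gives up is lost. They are not: one day of use is enough to stay in the set. Only complete never-users are affected.
- **Efficacy.** An at-least-one-use set is a defensible choice in an open-label, hypothesis-generating pilot, and the shift in the mean is small. Which set is primary for fatigue is partly a matter of choice.
- **A fuller SAP is promised.** It could add a set, but the documents contain none.

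**Conclusion.** The concern holds for the use and tolerability summaries, on the reading that clinic familiarisation is not use. On that reading the ever-use share can only be 100%, and mean use is overstated by 0% to 20% for 0 to 5 never-users among 30. The structural result follows from section 8.1 as written; the size rests entirely on an assumed k.

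A reader might go further and conclude that the fatigue result is seriously inflated. The planning figures do not support this: the shift is at most about 0.8 of a planned 5 points for k up to 5. That bound assumes never-users change by 0; it would be smaller if they also improved and larger if they worsened.

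**What to change.** Amend the analysis-set paragraph of section 8.1 as follows.

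1. Summarise use and tolerability outcomes for every participant given the device at Visit 1.
2. Count confirmed absence of home use as zero, and report log or technical failures separately as missing. The distinction matters because section 1.2 describes an on/off button on the device itself, section 7.1.2.4 anticipates technical problems at home, and section 6.5 does not say how gaps in the log will be recognised.
3. State that the Visit 1 familiarisation session does not count as use.
4. For PROMIS-Fatigue, report the change in all participants given the device who have a week-4 score, alongside the set with at least one day of use. State which is primary before the usage logs are reviewed.

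The cost is a short edit to one section plus a rule for telling non-use from a logging failure. The usage tracking and final-visit assessments are already planned. The downside is that the use figures, and possibly the mean change, may look slightly less favourable.

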8.2 Statistical and analytical plans

8.2.1 Demographic and other baseline characteristics

Demographic variables and baseline characteristics will be summarized by treatment group.

8.2.2 Efficacy

The primary endpoint is the mean change from baseline to end of the two-week intervention in the PROMIS-Fatigue questionnaire. For the primary analysis, changes in score will be compared in the two treatment groups using an repeated measures t-test. If the assumptions of this parametric model are not met, an alternative non-parametric model will be used. This model is based on the extension of the Wilcoxon rank-sum test to allow for covariate adjustment (9). This rank ANCOVA can provide additional power associated with baseline covariate adjustment, even when the outcome variable is not normally distributed 1(10).

Analysis for secondary outcome measures that are continuous will be performed using a similar approach as that for the primary endpoint. We will compare the change in each secondary outcome measure from baseline to week 2 using an ANCOVA model or its non-parametric counterpart if the model assumptions aren't met. Analyses of secondary outcomes measures that are discrete will be performed using Fisher's exact tests. Analyses of secondary outcome measure that are counts will be performed using Poisson regression.

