Diagnosis and main criteria for inclusion	
 ▪ Men or women aged 18 years and older, inclusive ▪ Systemic Sclerosis as defined by 2013 the American College of Rheumatology (ACR) / European League Against Rheumatism (EULAR) classification. ▪ Steady daily doses of any immunosuppressive medication, vasodilators, antidepressants and anxiolytic use for 4 weeks prior to baseline. ▪ PROMIS-fatigue score of at least 45 ▪ Currently owns and operates a smart phone regularly ▪ Ability to provide informed consent
Study Design	Open label, single-arm, single center US study
Type of control	None
Number of participants	30
Primary outcome variable	Change in the PROMIS-Fatigue scale at four weeks

30

Plan for statistical analysis

The planned sample size of 30 SSc participants is based on practical considerations to obtain estimates of the magnitude of treatment differences for efficacy and safety rather than a desired power for a pre-specified difference.

From similar studies on Rheumatoid Arthritis and Systemic Lupus Erythematosus, the improvement of T-score after treatment is about 5. The standard deviation for general population is 10. However, we are restricting our population to participants with fatigue T-scores of less than 54 (with low score indicating high fatigue). With the range of T-score reduced about half, we expect the standard deviation to be about 5. The effect size is expected to be 1 (5/5).

Using paired t-test, we have 86% power to detect the effect size of 1 when we recruit 30 patients at a significance level of 0.05. We asked the IRB for the option of increasing the number of patients to 40, which will give us about 81% power to detect a smaller effect size of 0.8 at a significance level of 0.05.

Descriptive statistics will be derived for all clinical variables, mean and standard deviation for continuous outcomes and percentages for categorical and dichotomous variables.

The primary outcome of interest is fatigue, as measured by the FACIT-Fatigue. We will compare the mean change from baseline and four weeks in a repeated measures model.

The p-values resulting from formal statistical tests will be interpreted from a hypothesis-generating, rather than a confirmatory framework.

Table of contents

1. Introduction	9
1.1 Background	9
1.1.1 Scleroderma (systemic sclerosis).....	9

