4. STUDY DESIGN

4.1 Design overview

This clinical trial is a single-center, open-label, single-arm study of 30 individuals with SSc and fatigue.

The study will allow for subjects to continue standard of care medications for the management of SSc as background therapy.

The study design consists of a single, four-week intervention. The screening and baseline visits can be combined when the screening is not able to be performed over the phone in advance.

- **Screening phase:** up to 4 weeks prior to baseline visit
- **Observation period:** During this one week phase participants will track their daily Raynaud attack frequency and duration using a diary. This will occur in the seven days preceding the baseline intervention phase.
- **Open-label intervention phase:** This consists of a four-week period during which participants will use the Apollo wearable system as needed to manage symptoms including fatigue. During the intervention phase participants may use the wearable at their discretion and control. Participants will track their daily Raynaud attack frequency and duration using a diary during week 4 of Apollo use. Participants will complete questionnaires on day 1 of the open-label and intervention phase, and at their follow-up four weeks later.

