6.2 Treatment assignment

This is an open-label, single-arm trial. No randomization or blinding will occur.

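### Section 8.2 keeps two-arm text in a single-arm trial: the primary paired test is recoverable, but the rank-based fallback and Fisher's exact test have no second group to compare

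*Combined protocol and SAP*

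**What the plan says.** The design is stated twice without ambiguity. Section 4.1: "This clinical trial is a single-center, open-label, single-arm study of 30 individuals with SSc and fatigue". Section 6.2: "This is an open-label, single-arm trial. No randomization or blinding will occur". The Synopsis gives the type of control as none.

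The analysis section assumes something else. Section 8.2.1: "Demographic variables and baseline characteristics will be summarized by treatment group". Section 8.2.2, on the primary endpoint: "For the primary analysis, changes in score will be compared in the two treatment groups using an repeated measures t-test". If the parametric assumptions fail, 8.2.2 switches to a covariate-adjusted extension of the Wilcoxon rank-sum test (rank ANCOVA), citing references 9 and 10. Continuous secondary outcomes are to be handled in a similar way to the primary, and the next sentence names ANCOVA. Discrete secondary outcomes are assigned to Fisher's exact test.

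The Synopsis names a within-person test: "Using paired t-test, we have 86% power to detect the effect size of 1 when we recruit 30 patients". Section 8.1 defers detail: "A statistical analysis plan (SAP) will be written for the study that contains detailed descriptions of the analyses to be performed". Its deadline is: "The SAP will be finalized prior to unblinding of the data".

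**The concern.** A method that compares groups needs a grouping factor, and this trial defines none. The two-group phrase in the primary sentence is only a leftover if the test itself is clear. The fallback and Fisher's test are different, because for them the second group is part of the method. Nowhere do the documents name a one-sample or paired alternative such as the signed-rank, sign or McNemar test.

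At stake is pre-specification. If the t-test assumptions are judged to fail, someone must invent a fallback for the primary endpoint. The SAP deadline does not prevent that from happening after outcomes are known, since all data are open from the start. The citations do not help to recover the intended method: in this reference list, item 9 is a cost-of-illness study of systemic sclerosis in France and item 10 is a palliative-care article on fatigue.

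**Working it through.** **1. Can the primary test be recovered?** Set three statements side by side: a repeated measures t-test (8.2.2), a paired t-test (Synopsis), and a comparison of baseline with four weeks in a repeated measures model (Synopsis). All three describe within-person change. Once the two-group phrase is dropped, a paired t-test remains.

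The Synopsis power figure does not itself support this reading. Inputs: n = 30, effect size 1, alpha 0.05 (two-sided, from 8.1).
- Paired t-test: noncentrality 1 × √30 = 5.48, 29 degrees of freedom, critical value 2.045. Power is 99.96%, not 86%. For n = 40 and effect size 0.8 it is 99.85%, not about 81%.
- Two independent halves, one-sided z: 1 × √(15/2) − 1.645 = 2.739 − 1.645 = 1.094, which gives 86.3%. For 20 per half and effect size 0.8: 0.8 × √(20/2) − 1.645 = 2.530 − 1.645 = 0.885, which gives 81.2%.

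So the name of the test points to a paired analysis, while the figures match a two-group calculation. This is consistent with two-arm carry-over, as is the drug-minus-placebo contrast left in section 8.5, but it does not prove it. The point made here does not depend on it.

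**2. Can the fallback be run?** The rank-sum statistic is the sum of one group's ranks in the pooled sample. With one group of 30 that sum is 30 × 31 / 2 = 465 for any data. Its null variance, n₁n₂(N + 1)/12, is 0 when n₂ = 0. In the covariate-adjusted form, the residuals from the rank regression sum to 0 for any data. Neither form carries information about whether fatigue changed.

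**3. Can Fisher's test be run?** It conditions on the margins of a group-by-outcome table. With one row, only one table has those margins, so p = 1 always. Using visit as the row would break the independence that the test needs, because the same people appear in both rows.

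**4. Is ANCOVA in the same position?** Not clearly. The sentence names no group and is ambiguous. A test of the intercept for change, adjusted for centred baseline, could be estimated in one arm.

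**5. Illustration only: visit used as the group.** Assumptions: 30 pairs, normal data, SD 5 at each visit, within-person correlation 0.3/0.5/0.7, two-sided 0.05, 20,000 replicates. The SD and the 5-point change come from the Synopsis. The correlations, the 2.5-point change and the use of visit as group are assumed.

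| Method | True null rejected | Power, 2.5-point change | Power, 5-point change |
|---|---|---|---|
| Rank-sum | 2.0% / 0.8% / 0.1% | 44% / 44% / 43% | 98% / 99% / 99.8% |
| Rank ANCOVA, baseline as covariate | about 7.8% / 7.0% / 6.6% | not given | 99.5–100% |
| Signed-rank | 4.9–5.0% | 59% / 73% / 91% | 99.3–100% |

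**6. The replacement under non-normal changes.** Assumptions: n = 30, true mean change 0, two-sided 0.05, illustrative distributions.
- Exponential changes: signed-rank rejects 16%, paired t about 7%.
- Lognormal changes (sigma 0.5): signed-rank 11–12%, paired t about 7%.
- Symmetric heavy tails (t, 3 degrees of freedom): signed-rank 4.8%, paired t about 4%.

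The signed-rank test is therefore a safe test of the mean change only when changes are roughly symmetric.

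**The case against.** The strongest reply is that the consequences are small and partly hypothetical. Section 8.1 says "As such the analysis will be largely descriptive in nature" and treats p-values as hypothesis-generating. Section 8 calls itself a summary, and the fuller SAP is not among the documents, so it may name a suitable fallback. The documents do not say which outcomes are discrete, and most listed outcomes are scores or counts, so Fisher's test may have little to act on. All of this stands and limits the weight of the point. It does not make the named methods executable: 8.1 still commits to two-tailed tests at 0.05 with p-values reported, and its SAP deadline secures nothing in an unblinded trial.

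A second reply concerns the simulation with visit as group. Those data are normal, the one setting in which the plan would not use the fallback, and no section makes visit the group. This also stands. The table shows how two improvised adaptations behave on normal data; it does not measure harm to this trial.

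A reader might go further and infer that the trial has no valid primary analysis. The documents do not support that, because the paired t-test is recoverable. Nor do they show that a method would in fact be picked after seeing the data; they only leave that open. Poisson regression for counts should not be added to the list either: no defect in it is shown here.

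**Conclusion.** Wrong as written, with limited harm. Sections 8.2.1 and 8.2.2 contradict the single-arm design. The primary paired t-test survives. The only named fallback for the primary endpoint and the only named test for discrete outcomes cannot validly be run, and that follows from the design alone, without any assumption about the data. The visible text has no effective deadline for choosing replacements.

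The size of the effect on the trial's result cannot be stated. It depends on whether the t-test assumptions are judged to fail, on what is substituted, and on which outcomes are treated as discrete, none of which the documents settle. In the normal-data illustration little is lost at the planned 5-point change, where every method has at least 98% power. The gap appears only at the assumed smaller change, and it should not be read as an estimate of harm when the fallback is triggered.

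**What to change.** - **8.2.2, primary:** delete the two-group phrase and the rank-sum/rank ANCOVA text with its mismatched citations. State a paired t-test of Visit 2 minus baseline, with mean change and 95% confidence interval, reported in all cases.
- **8.2.2, fallback:** name the Wilcoxon signed-rank test as fallback or sensitivity analysis. State that it tests the mean change only if changes are roughly symmetric, and otherwise targets a different measure of location.
- **8.2.2, secondary:** use the same approach for continuous outcomes in place of the ANCOVA sentence. Replace Fisher's test with exact McNemar for any outcome dichotomized by a rule fixed in advance.
- **8.2.2, timing:** the paragraph speaks of two weeks and week 2, while the Synopsis and sections 2 and 4.1 set the endpoint at four weeks. These passages must be reconciled in the same edit.
- **8.2.1:** delete the reference to treatment group.
- **8.1:** replace the unblinding deadline with a dated event, such as before any Visit 2 outcome data are reviewed.

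The cost is protocol and SAP wording only; no new data and no additional participants.
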